**Comparing Effectiveness of CSE Versus DPE for Labor Analgesia**

NCT05068661

3/22/2024

After obtaining written informed consent, parturients are randomised in a 1:1 ratio by computer-generated random sequence to CSE or DPE arms, stratified by parity (nulliparous versus multiparous) and class of obesity (BMI <40 vs. 40-50 kg.m^-2). Allocation is concealed in sequentially numbered opaque envelopes. Patients, obstetricians, nurses, and anesthesia providers involved in follow-up of labour analgesia and data collection are blinded to group allocation. The anesthesia provider placing the neuraxial block and the supervising attending anesthesiologist are not involved in data collection or in follow up of labour analgesia.

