The end time of administration of the loading dose (end of spinal dose injection in the CSE group or epidural medication administration in the DPE group) is designated time 0 ( $t = 0$ ). A blinded investigator collects data at 15 and 30 min and subsequently at 2-h intervals from time zero until delivery. Analgesia is evaluated at all time points using the verbal numeric pain rating scale (NPRS) for the last contraction (0=no pain, 10=worst possible pain). The upper and lower sensory levels are evaluated at 15 and 30 min using temperature discrimination to ice. Motor blockade is assessed at all time points using the modified Bromage score.

The following additional data are recorded every 2 h until delivery: presence of pruritus; nausea; hypotension (defined as systolic blood pressure  $\leq 20\%$  from the patient's admission blood pressure); need for physician top-up; catheter adjustment and catheter replacement. We also assess for the presence of asymmetric blockade, defined as a difference  $> 2$  dermatomal sensory levels between the left and right side as assessed at 15 and 30 min or at any time that sensory levels are checked because of complaints of pain. An obstetrician blinded to group assignments accesses the electronic medical record to review tocometry and continuous fetal monitoring strips and extract uterine contraction and fetal heart rate monitoring patterns in 10-min epochs, for 1 h before and 1 h after the initial spinal (CSE group) or epidural (DPE group) dosing. On the first postpartum day, we assessed for postdural puncture headache and satisfaction with labour analgesia (0-10, 0= very dissatisfied, 10=very satisfied)

The primary outcome of the study is the quality of labour analgesia, which is defined by a composite of five components: asymmetric block after 30 min of initiation (difference in sensory level of more than two dermatomes); epidural top-up interventions; catheter adjustment; catheter replacement; failed conversion to neuraxial anesthesia for cesarean delivery, requiring general anesthesia or replacement of the neuraxial block.

Secondary outcomes include: pain scores; Bromage scores; sensory levels at 15 and 30 min; adverse events (hypotension, nausea, pruritus, postdural puncture headache, fetal heart rate changes); duration of second stage of labor; mode of delivery; total anesthetic dose; PCEA use; and overall satisfaction with analgesia.

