Based on the study by Chau et al a sample size of 50 patients per group had an 80% power at alpha 0.05 to detect a reduction in the composite primary outcome from 50% in the CSE group to 22.5 % in the DPE group. To account for dropouts, we aim to enrol up to 60 patients per group to have complete data on 100 subjects.

Descriptive statistics for patient characteristics and outcomes are calculated and reported as median (IQR [range]) or number (proportion) as appropriate. The primary composite outcome is compared between exposure groups using a chi-squared test and an effect size is reported as a risk ratio. Secondary outcomes are assessed using chi-squared or Fisher exact tests as appropriate, with associated risk ratios for categorical measures and univariate log-linear regression with mean ratios for continuous measures. All p values for the secondary outcomes are adjusted for multiple comparisons using the Bonferroni-Holm method to control family-wise error rate and adjusted p values are reported. Only p values and adjusted p values < 0.05 are considered statistically significant. Analysis is performed using R version 4.3.1, with the power calculation performed using NQuery.

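### For a rare harm such as postdural puncture headache, the planned risk ratio may be undefined, zero or infinite at 50 women per arm; a risk difference with a score interval should be added for the adverse events

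*Combined protocol and SAP*

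**What the plan says.** The combined protocol and SAP has no numbered sections. Four places bear on the point.

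- **Secondary outcomes paragraph.** The list includes "adverse events (hypotension, nausea, pruritus, postdural puncture headache, fetal heart rate changes"). No expected rate is given for any of them.
- **Data collection paragraph.** Headache is looked for once: "On the first postpartum day, we assessed for postdural puncture headache".
- **Statistical paragraph, secondary outcomes.** "Secondary outcomes are assessed using chi-squared or Fisher exact tests as appropriate", "with associated risk ratios for categorical measures". No risk difference, odds ratio, interval method, zero-cell correction or fallback for sparse outcomes is named.
- **Statistical paragraph, descriptive statistics.** Outcomes are also "reported as median (IQR [range]) or number (proportion) as appropriate".

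The size of the trial comes from the sample size paragraph: "a sample size of 50 patients per group had an 80% power at alpha 0.05", for a fall in the primary composite "from 50% in the CSE group to 22.5 % in the DPE group". Complete data are sought on 100 women, from up to 60 enrolled per arm.

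**The concern.** A risk ratio needs events in the comparison arm to be finite, and in both arms to have the usual log-scale interval. The plan uses it as the only between-group measure for every categorical secondary outcome, whether common or rare. For a rare harm in 50 women per arm, one or both arms may well have no events.

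For such a harm, the useful result from a trial of this size is how large a difference it can rule out. A ratio of 0/0 says nothing on that, and a bare 0 or infinity says very little. The p value does not help either: Fisher's test gives p = 1.0 for 1/50 against 0/50 and p = 0.49 for 2/50 against 0/50, before the Bonferroni-Holm adjustment. A table showing only an undefined ratio and a non-significant p value invites the reading that the two techniques are equally safe, which 100 women cannot show for a rare event.

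**Working it through.** **Inputs.** From the documents: 1:1 allocation, 50 evaluable women per arm, up to 60 enrolled per arm, and 50% against 22.5% for the primary composite at 80% power and alpha 0.05 (taken as two-sided). Assumed, because the documents give no figure: the harm rate p, varied from 0.2% to 10% and equal in both arms unless stated. Equal headache rates are a reasonable base case because both arms have the same needle-through-needle dural puncture.

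**The plan's own figure.** The log-odds-ratio formula reproduces the 50 per group:

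- ln(OR) = ln[(0.225/0.775)/(0.5/0.5)] = -1.237, squared 1.530.
- Variance term = 1/(0.5 × 0.5) + 1/(0.225 × 0.775) = 4 + 5.735 = 9.735.
- n = (1.960 + 0.842)² × 9.735 / 1.530 ≈ 50.

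The usual pooled formula for the planned chi-squared test needs 47, so 50 is slightly generous for it. The document does not say which formula was used. None of this affects the present point; it confirms 50 as the denominator.

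**Probability that the ratio fails.** Let q = (1 - p)^50 be the chance of no events in one arm. Then:

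- P(0/0) = q²
- P(ratio is 0 or infinite) = 2q(1 - q)
- P(either) = 1 - (1 - q)²

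Example at p = 2%: q = 0.98^50 = 0.364. So q² = 0.133, 2 × 0.364 × 0.636 = 0.463, and the total is 0.596.

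| Assumed rate, both arms | Undefined (0/0) | 0 or infinite | Either |
|---|---|---|---|
| 0.2% | 82% | 17% | 99% |
| 0.5% | 61% | 35% | 95% |
| 1% | 37% | 48% | 84% |
| 2% | 13% | 46% | 60% |
| 3% | 5% | 34% | 39% |
| 5% | 0.6% | 14% | 15% |
| 10% | about 0% | 1% | 1% |

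The total exceeds one half when the rate is below about 2.4% per arm. With unequal rates it is 75% for 1% against 2%, 41% for 2% against 5%, and 64% for 1% against 5%. If all 60 per arm were analysed, it would be 80% at 1%, 51% at 2% and 9% at 5%.

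**What a risk difference would give.** The Miettinen-Nurminen interval exists for each of these tables. Adding 0.5 to the cells, a common repair of the ratio, is shown beside it.

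| Events | Raw risk ratio | Risk difference, points (95% Miettinen-Nurminen) | Risk ratio after adding 0.5 (95% CI) |
|---|---|---|---|
| 0/50 vs 0/50 | undefined | 0.0 (about -7.2 to +7.2) | 1.0 (0.02 to 49) |
| 1/50 vs 0/50 | infinite | 2.0 (about -5.3 to +10.6) | 3.0 (0.13 to 72) |
| 2/50 vs 0/50 | infinite | 4.0 (about -3.3 to +13.5) | 5.0 (0.25 to 102) |

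The risk difference states plainly that differences of several percentage points remain possible. In the empty table, the patched ratio reflects the correction rather than the data.

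**The case against.** The strongest reply is that little is lost. Several stronger readings are tempting, and the documents do not support them.

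- **That only a p value would be left.** This is wrong. Counts and proportions are planned for outcomes, and a reader given them by arm could work out a risk difference and an interval. What is missing is a prespecified between-group estimate that survives an empty arm.
- **That the ratio cannot be calculated whenever an arm is empty.** This is too strong. A ratio of 0 is a calculable estimate, and a score interval for the ratio exists with one empty arm: 0/50 against 3/50 gives 0 to 1.25. Only 0/0 is truly undefined, and it is the log-scale interval that breaks down in the one-empty-arm case. The plan does not prescribe that interval; it names none.
- **That allowing Fisher's test shows zero cells were expected.** It does not. The choice is conditional, and under the customary rule of expected counts below 5, Fisher's test applies at any rate below 10% with 50 per arm. At 10% an empty arm has a chance of about 1%.
- **That the ratio fails for the adverse events generally.** Nothing in the documents shows this for hypotension, nausea, pruritus or fetal heart rate changes, any of which may be common. Even the rarity of headache is an assumption.
- **That the risk ratio should give way for every binary outcome.** No defect is shown for the primary composite, planned at 50% against 22.5%, or for the other categorical outcomes.

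It is also fair to say that the plan claims neither equivalence nor safety, so the equal-safety misreading is a risk in how results are read, not something the plan asserts. What stands is narrow: for a harm rare enough to leave an arm empty, the one planned effect measure may be uninformative, and the choice of substitute would be made after seeing the data.

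**Conclusion.** The point holds as a minor reporting improvement, limited to rare harms. At 50 per arm and equal rates of 1% to 5%, the chance that the planned ratio is undefined, 0 or infinite runs from 84% down to 15%; the strictly undefined part runs from 37% down to 0.6%. These figures rest on assumed rates. Postdural puncture headache is the likely case, with a single first-day assessment that leaves later headaches uncounted, but its rate is not documented. The primary test, the sample size and the secondary p values are unaffected.

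**What to change.** Add to the statistical paragraph: 'For each binary adverse event, report the risk difference with a 95% Miettinen-Nurminen (score) confidence interval; also report the risk ratio with 95% CI where both arms have events.' Leave the risk ratio as the stated measure for the primary composite and the other categorical outcomes.

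The cost is one sentence and a standard R routine. It needs no new data and no change to the sample size, the tests or the multiplicity adjustment. In return, every adverse event has an interval showing what 100 women can and cannot exclude, and the handling of empty arms is fixed in advance.

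### Does putting the adverse events in the same Holm family as the other secondary outcomes make the safety comparison unsound?

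*Combined protocol and SAP*

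**What the plan says.** The analysis paragraph at the end of the Combined protocol and SAP sets a single rule: "All p values for the secondary outcomes are adjusted for multiple comparisons using the Bonferroni-Holm method to control family-wise error rate". It then fixes the cut-off: "Only p values and adjusted p values < 0.05 are considered statistically significant".

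The paragraph on secondary outcomes begins "Secondary outcomes include: pain scores; Bromage scores; sensory levels at 15 and 30 min" and goes on to "adverse events (hypotension, nausea, pruritus, postdural puncture headache, fetal heart rate changes", followed by second-stage duration, delivery mode, anesthetic dose, PCEA use and satisfaction. The adverse events therefore share one family with the analgesic and obstetric outcomes. No safety exemption or separate safety family is given, and the number of tests is not stated.

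The analysis paragraph also provides for categorical outcomes to be summarised as numbers with proportions, and for categorical secondary outcomes to carry a risk ratio. Neither depends on the test result. Confidence intervals are not mentioned.

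**The concern.** Family-wise error control limits false positive findings. For efficacy claims that is usually the error to guard against. For harms, many statisticians worry more about the opposite error, missing a real difference, and a multiplicity correction makes that error more likely.

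Here five maternal and fetal events are pooled with at least eight other outcomes. Pain and motor block are measured at 15 and 30 minutes and then every two hours until delivery. If each time were tested separately, the family would grow and the threshold for hypotension or fetal heart rate change would tighten for reasons unrelated to safety. With about 50 women per arm, the fear is that the report would find no significant difference in adverse events even where a large one exists, and that readers would take this as reassurance. The analgesic secondary outcomes would also lose some power by sharing the family with the adverse events.

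**Working it through.** **Inputs from the document.** Analysable sample: 50 per arm ("we aim to enrol up to 60 patients per group to have complete data on 100 subjects"), allocated 1:1. Significance level: 0.05, taken as two-sided because the test is chi-squared. Adverse events: 5.

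**Inputs that are assumptions.** All adverse event rates (the document gives none), and any family size above 14.

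**The plan's own figure.** The plan states that "a sample size of 50 patients per group had an 80% power at alpha 0.05" to detect a fall "from 50% in the CSE group to 22.5 % in the DPE group". The power formula used throughout is Φ[(d − z·s₀)/s₁], with s₀ = √(2p̄(1−p̄)/n) and s₁ = √((p₁(1−p₁)+p₂(1−p₂))/n). Here d = 0.275, p̄ = 0.3625, s₀ = 0.0961 and s₁ = 0.0921. Power is Φ[(0.275 − 1.960×0.0961)/0.0921] = Φ(0.94) = 82.6%. The uncorrected test needs 47 per group for 80%, Fisher's exact test about 53 and the continuity-corrected test 54. The stated 50 lies between these. The small mismatch has no bearing on this point.

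**Family size.** The list gives pain 1, Bromage 1, sensory level 1, adverse events 5 and other outcomes 5, which is 13. Counting sensory level at both times gives 14. Reaching 26 requires, for example, six pain times, six Bromage times and four sensory tests (6 + 6 + 4 + 5 + 5). The document neither fixes the number of times nor says that each is tested.

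**First Holm step.** 0.05/13 = 0.0038; 0.05/14 = 0.0036; 0.05/26 = 0.0019.

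**Power at 50 per arm.** For 10% versus 30%: d = 0.20, s₀ = 0.0800, s₁ = 0.0775. At 0.05, Φ[(0.20 − 1.960×0.0800)/0.0775] = Φ(0.56) = 71%. At 0.05/14, z = 2.914 and Φ(−0.43) = 33.5%. The other rows use the same formula.

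| Assumed rates | 0.05 | 0.05/5 | 0.05/14 | 0.05/26 |
|---|---|---|---|---|
| 5% vs 20% | 62% | 38% | 25% | 20% |
| 10% vs 30% | 71% | 47% | 34% | 27% |
| 5% vs 25% | 81% | 59% | 45% | 38% |
| 10% vs 40% | 95% | 83% | 72% | 65% |
| 20% vs 60% | 99% | 95% | 90% | 86% |

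The loss is real for gaps of 15 to 20 points and much smaller for the widest gaps. It is not true that any large difference would probably be missed. For 10% versus 30%, the chance of missing the difference is already 29% with no adjustment, because of the sample size.

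**Why 0.05/14 is the strictest case.** Only the smallest p value in the family meets 0.05/m. After k rejections the next threshold is 0.05/(m − k). With 14 tests and five rejections it is 0.05/9, where power for 10% versus 30% is 39%. After nine rejections it is 0.05/5, where power is 47%.

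**Price of taking the events out.** Five unadjusted tests give 1 − 0.95⁵ = 22.6% for at least one false signal if they are independent.

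**Gain for the other outcomes.** Removing five tests moves their first step from 0.05/14 = 0.0036 to 0.05/9 = 0.0056. This gain comes from giving up family-wise control over the five events.

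**What is being compared.** Both arms receive an active neuraxial technique. An excess of pruritus, hypotension or fetal heart rate change in one arm is at the same time a claimed advantage for the other. Guarding against false claims is therefore relevant to these outcomes too.

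**The case for a change.** The strongest case for the concern is that the Holm relaxation recovers little. Even after nine rejections, power for 10% versus 30% is 47% against 71% unadjusted. Fisher's test, which the plan also allows, shows the effect in counts. With no events among 50 in one arm, six of 50 in the other reach significance at 0.05 (p = 0.027), but nine are needed at 0.05/14 (p = 0.0026). Eight give p = 0.0058 and would not be called significant at that step. The plan gives no specific reason for treating harms this way, leaves the family size open and does not mention intervals.

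The figures stand, and a separate safety family or unadjusted safety comparisons would also have been defensible. But this is a preference between two error rates, and the plan has chosen one openly and in advance. A result of 0/50 against 8/50 would still appear in the report as counts and proportions, whatever its adjusted p value, and a reader could work out an unadjusted interval for the difference from those counts. Reading a non-significant result as proof of equal safety would be wrong, but the document does not do so. The missing family size and intervals are gaps in detail that ordinary reporting fills. They do not make the method incorrect.

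**Conclusion.** No error. The adverse events are in the Holm family, and this costs power: at the first of 14 steps, from 71% to 34% for 10% versus 30%, and from 81% to 45% for 5% versus 25%. These figures rest on assumed event rates, on 50 complete women per arm and on the adverse event facing the strictest step. The figure of 26 tests also rests on assumed time points; the document's own list supports 13 or 14.

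Against that cost stands family-wise control over comparisons in which either arm can gain from a chance finding. The alternative carries about a 23% risk of at least one false signal among the five events, assuming independence. The choice is prespecified, consistent throughout the document and does not touch the primary analysis. The effect estimates for harm are reported in any case.
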